**Option 1**

**Describe how your study meets these criteria:**

a) The only record linking the participant and the research would be the consent document:

b) The principal risk would be potential harm resulting from a breach of confidentiality (i.e., a study that involves subjects who use illegal drugs).

Under this option, each participant (or legally authorized representative) must be asked whether (s)he wants to sign a consent document; if the participant agrees to sign a consent document, only an IRB approved version should be used.

**Option 2**

**Describe how your study meets these criteria:**

a) The research presents no more than minimal risk to the participant:

b) Involves no procedures for which written consent is normally required outside of the research context (i.e. a cover letter on a survey, or a phone script):

**Option 3**

**Describe how your study meets these criteria:**

a) The subject (or legally authorized representative) is a member of a distinct cultural group or community in which signing forms is not the norm.

b) The research presents no more than minimal risk to the subject.

c) There is an appropriate alternative mechanism for documenting that informed consent was obtained.

## RESEARCH DESCRIPTION

0 unresolved  
comment(s)

You may attach a sponsor's protocol pages in the "Additional Information" section and refer to them where necessary in the Research Description. However, each prompt that applies to your study should contain at least a summary paragraph.

## Pro Tips:

- Save your work often to avoid losing data.
- Use one of the attachment buttons in this section or under the Additional Information section to include supplemental information with your application. During the document upload process, you will be able to provide a brief description of the attachment.

## Background

Include a brief review of existing literature in the area of your research. You should identify gaps in knowledge that should be addressed and explain how your research will address those gaps or contribute to existing knowledge in this area. For interventional research, search PubMed and ClinicalTrials.gov for duplicative ongoing and completed trials with same condition and intervention(s).

**Background and Significance.** Childhood undernutrition (low weight for age, low height for age, low weight for height, or micronutrient deficiencies) contributes up to 45% of deaths globally in children under five years and negatively impacts individual and societal health by impairment of long-term health, cognitive capacity, productivity and wage-earning force. Identification of effective, locally available, low-cost, and readily scalable interventions for its prevention remains elusive. Undernutrition may begin in utero due to maternal undernutrition and micronutrient deficiencies. After birth, poor nutrient intake, frequent infectious disease, and poor intestinal health lead to ongoing impaired growth and psychomotor-cognitive development. Intestinal inflammation and reduced gut integrity from chronic exposure to intestinal pathogens leads to Environmental Enteric Dysfunction or EED (aka "tropical sprue"). Large-scale research has increasingly established the role of intestinal inflammation and a leaky gut in stunting, reduced efficacy of oral vaccines, reduced absorption of nutrients, intestinal dysbiosis, and increased morbidity and mortality in childhood undernutrition.

Early intervention within the first 1000 days of life from conception to 24 months may mitigate or reverse the adverse impact of undernutrition and its associated complications. Interventions after 24 months are additionally important to prevent or reverse worsening undernutrition. Potential targets include improving breastmilk quality and quantity for exclusively-breastfeeding infants, increasing the nutrient density of complementary foods for infants and children over 6 months of age, and optimizing intestinal and systemic inflammation to improve nutrient absorption and reduce nutritional needs in all age groups. Accessible and practical interventions that address multiple determinants of undernutrition in regions with high prevalence of maternal and child undernutrition such as the western Kenyan state of Kisumu are a priority.

*Moringa oleifera* (*moringa*) is a drought-resistant, rapidly growing, and extremely nutrient dense tree suitable to household- or community-level cultivation in many regions with high rates of childhood and maternal undernutrition. *Moringa* leaves are a promising local resource to supplement existing low-quality diets with high concentration of complete protein (30g/100g dried leaf), iron (97.9 mcg/g dried leaf), Vitamin A precursors (17.6-39.6mg/100g dried leaf) as well as B vitamins, calcium, and many other essential nutrients and fiber at very low cost. In addition, medicinal claims under investigation demonstrate antimicrobial properties and impacts on metabolism and inflammation including reduced intestinal inflammation in models of colitis. Veterinary and agricultural data have long shown improved lactation, growth, reduced infection, and increased litter yields in animals; however, human studies have been limited in scope, consistency, and quality for this and for the evaluation of micronutrient changes. Limited clinical research shows increased vitamin A levels in infants supplemented directly with low dose (5g) *moringa* leaf powder with mixed impact on iron levels; adult studies suggest improvements in iron deficiency anemia with differing doses of high dose daily but not weekly *moringa* leaf powder supplementation. Animal studies examining *Moringa* leaf supplementation and its impact on breastmilk antioxidants show improved antioxidant catalase activity and vitamin C concentration and decreased marker of fatty acid oxidation malondialdehyde in 25% *moringa* leaf supplementation to ewes compared to standard alfalfa hay diet in addition to increased milk yield. Dairy cows supplemented with 6% *moringa* leaves show increased milk fat content and improved unsaturated fatty acid concentration with no changes in protein content. Human studies assessing changes in breastmilk composition with *moringa* supplementation are not available.

**Relevance to Kisumu, Kenya:** Our target subjects of Kisumu, Kenya are a rural population with poor water, sanitation, hygiene, high rates of undernutrition and limited access to health resources. They have low Dietary Diversity (availability of adequate varied food groups) leading to additional micronutrient deficiencies. They are mostly subsistence farmers who are not universally acquainted with *moringa* cultivation or consumption, however we have recently completed a study in Kisumu that shows excellent acceptance and uptake of *moringa* intensive leaf cultivation and a positive attitude to dried leaf powder consumption ([name] and [name], manuscript in progress 2020). The wider Kisumu population is the target area of our partner Pamoja Community Based Organization (Pamoja, executive director [name]), which spans three districts in the region of Kisumu comprising some of the highest-needs populations in Kenya. In a 2019 baseline survey of 469 0-59 month old children within Pamoja's catchment area, 25% were stunted, 8% wasted, and 13% underweight (unpublished data, personal communication from [name]). Micronutrient deficiencies are not specifically defined in this population, however an estimated 69% of children under five years in Kenya are iron deficient and 20-39% are estimated to have vitamin A deficiency. Targeting undernutrition in a cost-effective manner is crucially needed in this region; our study will work with the infrastructure and trust of Pamoja and the communities it serves by testing acceptability of *moringa* leaf consumption in staple food of grain porridge, acceptability of placebo, and conducting a pilot of *moringa* leaf consumption and its effect on childhood growth, nutrition, and intestinal and systemic inflammation.

**Safety:** No trial of *moringa* leaf consumption in children or lactating women has shown significant adverse effects. Cultures all over the world and across centuries have used *moringa* leaf as food and medicine without reported ill effect at traditional doses. Seed, root, or leaf extract are not the intervention used in this study. They concentrate the biochemically active plant isothiocyanates and phytosterols

and have medicinal effects and may potential toxic effects at extremely high doses. Moringa leaf powder has not yet been shown to interact with HIV medications, and preclinical studies even raise the possibility of improvements in immune function for HIV affected individuals. However unlikely, any serious and unexpected adverse event will be reported to the IRB according to current protocol. Innovation. Studies to date on the effects of moringa in diabetes and anemia and animal studies that examine the utility of moringa for increased milk and litter yield are of small scale, however high quality large-scale placebo or case-controlled clinical trials to define the impact on infants of moringa leaf powder consumption by breastfeeding mothers are lacking. Moringa has a traditional and agricultural history of use as a galactagogue; despite this and its incorporation into products such as Mother's Milk Tea© and placement on NIH LactMed Lactation Database, this property has not been studied in large clinical trials nor in populations dependent on breastmilk such as in Kisumu. This study will improve and add to existing knowledge of moringa's effect on human breastmilk and will provide novel information on the effect of moringa supplementation to lactating mothers on their infant's intestinal inflammation and health. Further understanding of the acceptability of moringa leaf in a staple food of porridge and more the effect of moringa supplementation on infant and childhood growth, nutrition, and intestinal and systemic inflammation may translate in the future to the cultivation of moringa at the community or household level as an effective resource for the improvement of childhood undernutrition.

Ethical Approval: We have obtained Reliance agreement with University of California, Davis. We will obtain ethical approval from Amref Health Africa Ethics and Scientific Review Committee (application submitted).

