**Phase B) Pilot RCT**

Inclusion criteria: lactating women of at least 18 years of age and their exclusively breastfed infants within 30 days of delivery with informed consent. Children 6-59 months who are orally feeding with caregiver informed consent.

Exclusion criteria: regular maternal consumption of moringa in the month prior to study enrollment, receipt and consumption of food supplementation program, or inability to feed orally; for infant, significant congenital disease, inability to feed orally. For child: inability to feed orally or refusal to eat porridge (>3 days consecutively).

We anticipate enrolling up to 50 mother-infant dyads in each of two arms and 50 children in each of two arms.

We propose starting enrollment as soon as all ethical approvals obtained, personnel hired, and study supplies obtained; there is no additional sample composition of subjects. This study targets women and infants as breastfeeding infants have the potential to receive the greatest benefit from moringa leaf supplementation to their lactating mothers.

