**SECTION 2. Assessment and Evaluation of the Risks**

For details, refer to the UK IRB's [Policy on Children in Research](#).

A. Provide justification for the participation of children as research subjects in your study.

We are investigating the effect to their infants of moringa oleifera leaf supplementation to breastfeeding mothers. Infants are thus required participants

B. Has this research been conducted in adults?  Yes  No

If yes, is there any indication that the proposed research would benefit, or at least not be harmful to children?

Multiple generations of traditional use of moringa oleifera by adults, children, animals; many studies utilizing moringa oleifera leaf with no significant safety concern to breastfeeding mother or children

C. Indicate how many children you propose to enroll in the study: 320

**Note:** Whenever possible, involve the fewest number of children necessary to obtain statistically significant data which will contribute to a meaningful analysis relative to the purpose of the study.

Justify this number:

In the United States as an example of a mostly well-resourced population, stunting prevalence in children under five years is 3.5% (UNICEF data from last census 2016).(44) In comparison, in a 2019 cross-sectional survey of Pamoja CBO recipient population in Kisumu (unpublished data, Pamoja CBO 2019) stunting prevalence is 25% in children <5 years. This is comparable to the most recent national level Kenyan data of the region that contains Kisumu (Nyanza region) from the 2014 Kenyan National Demographic Health Survey showing a stunting prevalence of 24.9% in children <5 years of age.(45) We hypothesize that we will see a 75% reduction in stunting prevalence (<-2 LAZ) at 3 months of age in children with moringa-supplemented breastmilk versus controls. We think that moringa supplementation will

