increase breastmilk volumes thus increasing infant growth and may lead to improved intestinal health leading to increased absorption of nutrients consumed. Thus, we estimate a change from estimated 25% stunting prevalence to 6.5% stunting; in comparison, this is still double the prevalence of stunting in children under five years in the United States (3.5% UNICEF data 2016). At 80% power, this would require a sample size of 82 infants in each arm. Due to concern for loss to follow up and a possibility of a smaller effect than estimated, we aim to recruit 100 infants in each arm if external funding is obtained. That is 200 infants. We also estimate 50 children 6-59 months in each arm, that is 100 children. We also estimate 10-20 children trying moringa and placebo for the acceptability study. That is a total of 320 children.

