Head circumference: A standard measuring tape will be extended from the broadest part of forehead to the broadest part of the back of the head for infants. A mean of three consecutive measurements will be recorded to the nearest 0.1cm.

Standardization: For infants and children, weight for age, weight for length/height, and length/height for age will be compared to WHO standard deviation tables or Z scores and assigned their Z score. Wasting is low weight for length/height; stunting is low length/height for age; underweight is low weight for age. These are all measures of undernutrition. Mild undernutrition is defined for any of those parameters as <-1 to and including <-2; moderate undernutrition is <-2 to and including -3; severe undernutrition is <-3. Infants or children with Severe Acute Malnutrition defined as severe wasting (weight or length for height <-3), and/or the presence of nutritional edema will be referred to the nearest nutritional rehabilitation center for treatment as per standard WHO protocol. For mothers, Body Mass Index will be calculated (weight / height squared in metric units) and MUAC recorded.

Quality Control: Participants will be consecutively measured by the same instruments. The study coordinator will perform monthly quality control assessing variance between measurers for all measurements in order to ensure consistent measurement. Retraining and observed measurement will occur for any inconsistencies. Patients who do not arrive for their monthly visits will be contacted to remind them if contact information is available, and then visited at home if unable to come to the health center.

Vitamin A: serum retinol binding protein will survey infant vitamin A levels as an efficient measure of vitamin A at the individual level.

(46,47) Other assays of vitamin A are more informative at the population level. Measurement of the systemic inflammatory marker CRP (C-reactive protein) will allow for assessment of Vitamin A with and without correction for inflammation.

Iron: low hemoglobin is a proxy of childhood iron deficiency utilized internationally by UNICEF in LMIC. Iron levels can be measured via their transporters and intermediate forms. Calculation of a transferrin receptor-ferritin index from ferritin and soluble transferrin receptor will lessen the impact of fluctuations in ferritin from inflammation.(48,49)

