## Statistical Analysis Plan – 58219

Statistical Analysis: Data analyses were performed using SPSS v28 (IBM Corp. 2021) with graphing via SPSS and Prism GraphPad (v9.5.1). Using an intention-to-treat approach, we performed univariate and multivariable analysis for primary and secondary outcomes as change from baseline per individual/group and between groups. We used Pearson's (for normally distributed data) or Spearman's (for non-normally distributed data) correlation to examine relationships between continuous variables, Pearson's chi square and Fisher's exact tests between categorical variables, and independent t-test or Mann-Whitney U test between binary and continuous variables as appropriate. Paired samples t-tests or Wilcoxon matched-paired sign-rank test were used for paired data. Continuous variables are presented here as mean with standard deviation (if normally distributed) as mean  $\pm$  SD or median with interquartile range (if not normally distributed) as median, IQR, while categorical variables are presented with counts and percentages. An alpha-level of 0.05 was used to determine significance. All enrolled participants who continued study activities through at least the first month were analyzed regardless of loss to follow up.

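### Infant Z scores carry no stated allowance for gestational age and preterm infants are eligible, so apparent stunting and within-arm growth change partly reflect early birth; the arm contrast stays unbiased but noisier.

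*Combined protocol and SAP*

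**What the plan says.** - **Rationale** (Background). "Undernutrition may begin in utero due to maternal undernutrition and micronutrient deficiencies".
- **Eligibility** (Phase B) Pilot RCT, repeated under Study Design). Exclusively breastfed infants enter within 30 days of delivery. The exclusions that concern the infant's own condition are "for infant, significant congenital disease, inability to feed orally". There is no limit on gestational age or birth weight.
- **Scoring** (Data Collection & Research Materials, Standardization paragraph). For infants and children, "length/height for age will be compared to WHO standard deviation tables or Z scores and assigned their Z score". The text does not say whether age is counted from birth or corrected for weeks of prematurity.
- **Target** (Subject Children, Section 2.C). The only growth hypothesis with numbers is a "75% reduction in stunting prevalence (<-2 LAZ) at 3 months of age", sized on the statement that "we estimate a change from estimated 25% stunting prevalence to 6.5% stunting".
- **Analysis** (Statistical Analysis Plan – 58219). Outcomes are analysed as change from baseline, per individual or group and between groups. Paired tests are listed for paired data. Multivariable analysis is mentioned, but no covariate is named.
- **Data items.** None of the text available mentions gestational age, birth weight, preterm birth or corrected age. The data collection tools and the timeline and outcome tables are listed as attachments, but their content is not shown.

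**The concern.** If age is counted from birth, an infant born several weeks early is compared with infants who have had those extra weeks of growth. Its length-for-age is then low at enrolment and at three months for a reason unrelated to nutrition after birth. Two reported quantities are affected.

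The first is the count below -2 LAZ, which then includes some infants because of early birth. The second is the change from baseline. A preterm infant that catches up shows a large gain in whichever arm it sits, so a paired within-arm test can show improvement with no effect of moringa. In the between-arm comparison the same gain is extra variance, which matters with up to 50 dyads per arm (Phase B) Pilot RCT).

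**Working it through.** **The plan's own figure.** Section 2.C states "At 80% power, this would require a sample size of 82 infants in each arm", for 25% against 6.5%. With two-sided alpha 0.05, 1:1 allocation and the usual two-proportion formula, I get 60 per arm, or 71 with continuity correction. The stated 82 is close to the 80 per arm needed for 90% power; power at 82 is 90.9%. That mismatch is a separate matter. The rates 25% and 6.5% are used below as the plan gives them.

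**Assumptions not in the documents.** 10% of infants preterm; early length gain 0.75 cm per week (0.65 to 0.85); LAZ SD equivalent to 2.0 cm; birth 3 to 6 weeks early; extra catch-up of 1.0 LAZ over three months; SD of the LAZ change 0.80.

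**Step 1: shift in LAZ when age is counted from birth.** Shift = weeks early × cm per week / 2.0.
- 3 weeks: 3 × 0.75 / 2.0 = 1.125.
- 6 weeks: 6 × 0.75 / 2.0 = 2.25 (1.95 to 2.55 over the range of gain).

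The 3-week case lies at the edge of the usual 37-week limit, so it serves as a lower bound.

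**Step 2: chance that a preterm infant scores as stunted, at the plan's rates.** P = Φ(Φ⁻¹(rate) + shift), with Φ⁻¹(0.25) = -0.674 and Φ⁻¹(0.065) = -1.514.

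| Shift | 25% arm | 6.5% arm | Difference among preterm infants |
|---|---|---|---|
| 0 | 25% | 6.5% | 18.5 points |
| 1.125 | 67% | 35% | 33 points |
| 2.25 | 94% | 77% | 17 points |

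**Step 3: added apparent stunting in each arm.** Added = 0.10 × (P − rate).
- 6.5% arm: 0.10 × (0.349 − 0.065) = 2.8 points, up to 0.10 × (0.769 − 0.065) = 7.0 points.
- 25% arm: 0.10 × (0.674 − 0.25) = 4.2 points, up to 0.10 × (0.942 − 0.25) = 6.9 points.

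The overall rates become 29.2% against 9.3% (difference 19.9 points) or 31.9% against 13.5% (difference 18.4 points). The planned difference is 18.5.

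**Step 4: power for the stunting comparison.** At 82 per arm, power is 90.9% with no shift, 90.5% with the smaller shift and 80.8% with the larger. At 50 per arm it is 72.5%, 71.9% and 59.4%.

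**Step 5: change score.** With preterm share p and extra catch-up g, variance = 0.80² + p(1 − p)g². For p = 0.10 and g = 1.0 this is 0.64 + 0.09 = 0.73, so the SD is 0.854. Information lost = 1 − 0.64/0.73 = 12%. The range is 2% to 31% for p from 5% to 15% and g from 0.5 to 1.5. The standard error of the arm difference at 50 per arm goes from √(2 × 0.64/50) = 0.160 to √(2 × 0.73/50) = 0.171. Chance imbalance in preterm infants is already part of that increase and is not a further loss.

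**Step 6: within-arm artefact and type I error.** Catch-up adds p × g to the mean change in each arm: 0.10 × 1.0 = 0.10 LAZ here, with an expected arm difference of zero. In simulation at 50 per arm with no treatment effect and 5% to 15% preterm, the between-arm t-test rejected in 4.8% to 5.0% of trials, against the nominal 5%.

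**The case against.** The strongest reply is that this is a placebo-controlled randomised trial. Prematurity and catch-up are equal in expectation across arms, so the treatment contrast is unbiased and its type I error is intact. That stands. A reader might infer that catch-up would be mistaken for a moringa effect; the design rules this out for the between-arm comparison, and only within-arm change is exposed.

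A reader might also infer that preterm infants are stunting events which moringa cannot remove. Under a uniform shift this fails: Step 2 still shows differences of 33 and 17 points among them. It would hold only if every preterm infant were below -2 LAZ in both arms.

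Nor does the Background sentence contradict the use of WHO tables. It concerns maternal and fetal undernutrition, which can affect a term infant and which a correction for prematurity would not remove.

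Two further replies stand in part. The unseen collection tools may record gestational age, and the unnamed covariates may include it. Yet the Standardization paragraph would still not say which age is used, and the SAP would still not say how the variable enters. Second, making corrected age the main analysis is a trade-off. A clinic-card date wrong by two weeks moves LAZ by 2 × 0.75 / 2.0 = 0.75, and a 37-week cut makes the score jump at the threshold. Corrected age therefore belongs in a sensitivity analysis.

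**Conclusion.** The point holds as one of precision and interpretation, not of bias. The documents leave the age used for infant Z scores undefined, admit preterm infants, and report within-arm change that includes their catch-up.

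The size rests on assumptions, since no preterm rate, catch-up gain or change SD is given. With 10% preterm, the higher apparent stunting is of the same order as the 6.5% target, yet the arm difference hardly moves. Power is almost unchanged for the smaller shift and about 10 points lower at 82 per arm for the larger. For change in LAZ the loss is about 12% of the information.

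The documents do not support the reading that all prematurity is scored as stunting: only preterm infants whose uncorrected LAZ falls below -2 are affected. They also do not establish that gestational age goes unrecorded.

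**What to change.** - **Statistical Analysis Plan.** Make the infant growth analysis a between-arm comparison of exit LAZ, adjusted for enrolment length (or LAZ) and age at enrolment. Draw no growth conclusion from paired within-arm change.
- **Covariates.** Copy gestational age and birth weight from the clinic card where available, and name them as covariates with a stated rule for missing values.
- **Data Collection & Research Materials, Standardization paragraph.** State which age is used to read the Z scores. Report corrected-age Z scores for infants known to be born before 37 weeks as a sensitivity analysis.

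The main adjustment needs no new measurement: enrolment length is already planned, and age at enrolment is needed for the Z score. The cost is two extra fields and SAP wording. The SAP is written in the past tense and the protocol describes infants already enrolled, so for them this means a re-analysis, labelled as such. The planned recall at 8 to 12 months offers a chance to check cards. The downside is that card-based gestational age is imprecise and will be missing for some infants.
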